4.8 Safety Evaluation

All safety summaries and analyses will be based upon the SP as defined in [Section 4.4](#).

4.8.1 Extent of Exposure

Exposure as measured by duration of treatment will be summarized by treatment group. Extent of exposure will be calculated for the Treatment Period (up to Week 26).

Days of exposure will be calculated for each subject: (date of last dose of treatment drug – date of first dose + 1).

The duration of study participation including the follow-up period will also be summarized by treatment group.

The duration of study participation will be calculated as (the latest of (last visit/follow-up date or study termination date) – randomization date + 1. For subjects who die during the study, time of study will be calculated as (date of death – randomization date) + 1.

4.8.2 Adverse Events

AEs will be coded using MedDRA (Version 18.1) with reference to SOC and PT. All of the displays will be summarized by SOC and PT unless otherwise specified.

The following AE summaries will be presented by treatment group:

- Number and percentage of TEAE
- Number and percentage of treatment related TEAE

- Number and percentage of TEAE by SOC, PT, and severity
- Number and percentage of treatment related TEAE by SOC, PT, and severity
- Number and percentage of TEAE by SOC, PT, and relatedness
- Number and percentage of Serious TEAE
- Number and percentage of Serious treatment related TEAE
- Number and percentage of TEAE leading to discontinuation
- Number and percentage of TEAE with fatal outcome

All AE summaries will provide the number of subjects reporting at least 1 adverse event and the total number of events reported.

General Rules for Adverse Events

1. An AE will be considered a TEAE if it begins on or after the first study drug dosing or that worsens in severity after at least 1 dose of study drug has been administered. In case of insufficient information to determine if the event occurred before, during or after study drug dosing, the AE will be considered treatment-emergent.

The imputation method for the handling of missing or partial dates will be as follows:

Start dates

- If the day is missing, but month and year are present and the same as the month and year of the first dose of study drug, then day will be set to the same day as the start of study drug. Otherwise this will be imputed as the first day of the month
- If the month is missing, but year is present and the same as the year of the first dose of study drug, then month will be set to the same month as the start of study drug. Otherwise this will be imputed as January
- If the year is missing, the event will be considered as treatment emergent and no imputation of the date will occur

Stop dates

- If the day is missing, this will be imputed as the last day of the month
 - If the month is missing, this will be imputed as December
 - If the year is missing, the adverse event will be considered as ongoing and no imputation of the date will occur
2. Subjects will be classified as having withdrawn from the study due to an AE if the subject had a study drug action taken recorded as “drug permanently withdrawn” on the Adverse Events page of the eCRF or subject had the Subject Status item recorded as ‘Dropout’ with ‘AE’ as the primary reason for premature study termination on the Final Subject Disposition page of the eCRF.
 3. Events occurring during the pre-treatment phase will not be reported/summarized but will be listed.
 4. If a subject experiences the same AE (i.e. same PT) more than once, all occurrences will be counted only once under the count for PT.
 5. If a subject experiences more than one AE in a particular SOC, they will only be included once in the count for the SOC, but will appear in the count for each appropriate PT within the SOC (unless it is the same PT).
 6. AEs related to study drug tables will include only those AEs with a relationship to study drug of ‘probably related’, ‘possibly related’, ‘not assessable’, or if there is a missing relationship on the AE page of the eCRF.
 7. For AE severity, when there is more than one AE of the same PT, the worst severity will be considered in the summary tables by severity

The AEs will be ordered by decreasing frequency, then alphabetically, for total subjects for each SOC and PT within an SOC.

An overall summary of AEs will be provided by treatment group and overall. The summary will include incidences for the following:

- Any TEAE
- Any Treatment Related TEAE
- Any Serious TEAE
- Any Treatment Related Serious TEAE
- Any TEAE leading to Study Discontinuation

- Any TEAE with Fatal Outcome

A listing of all TEAEs will be provided. Non-treatment-emergent AEs will be shown in a separate listing. These listings will be presented by treatment group and will include: site, subject identifier, adverse event (SOC, PT, and verbatim term), date of onset, date of resolution, duration, severity, seriousness, action taken, outcome and causality.

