5 STUDY DRUG

5.1 Identity

5.1.1 Investigational Treatment: SUVN-502 and Matching Placebo

From Day 1 to the end of Week 26, eligible subjects will receive double-blind oral administration of one of following three treatments:

- SUVN-502 50 mg
- SUVN-502 100 mg
- placebo

During the single-blind placebo washout period (Weeks 27 to 30), all subjects will receive placebo.

[REDACTED]

[REDACTED]	[REDACTED]	[REDACTED]	[REDACTED]	[REDACTED]
[REDACTED]	[REDACTED]	[REDACTED]	[REDACTED]	[REDACTED]
[REDACTED]	[REDACTED]	[REDACTED]	[REDACTED]	[REDACTED]
[REDACTED]	[REDACTED]	[REDACTED]	[REDACTED]	[REDACTED]
[REDACTED]	[REDACTED]	[REDACTED]	[REDACTED]	[REDACTED]
[REDACTED]	[REDACTED]	[REDACTED]	[REDACTED]	[REDACTED]
[REDACTED]	[REDACTED]	[REDACTED]	[REDACTED]	[REDACTED]
[REDACTED]	[REDACTED]	[REDACTED]	[REDACTED]	[REDACTED]

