6.2.1.2 Definitions

An AE is any untoward medical-occurrence that occurs in a subject or clinical investigation subject administered a pharmaceutical product, and which does not necessarily have to have a causal relationship with this treatment. An AE can therefore be any unfavorable and unintended sign (including abnormal laboratory finding), symptom, or disease temporally associated with the use of an investigational product, whether or not considered related to the product.

All AEs, including intercurrent illnesses, occurring during the study will be documented in the eCRF. Concomitant illnesses, which existed before entry into the study, will not be considered AEs unless they worsen during the treatment period. All AEs, regardless of the source of identification (e.g., physical examination, laboratory assessment, ECG, reported by subject), must be documented.

Pre-existing conditions will be recorded in the eCRF on the Medical History or appropriate page.

A treatment-emergent AE (TEAE) will be defined as an AE that begins or that worsens in severity after at least one dose of study drug has been administered.

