6.2.1.4 Recording Adverse Events

The period for adverse event reporting will extend from signing of informed consent until 14 days after the last study treatment administration (including placebo during the single-blind placebo washout period). Adverse events occurring after the end of the study should be reported to the Sponsor or Sponsor's designee by the Investigator if the Investigator considers there is a causal relationship with the study drug.

All AEs, regardless of the relationship to study drug, will be recorded in the eCRF. All AE reports should contain a brief description of the event, date and time of onset, date and time of resolution, intensity, treatment required, relationship to study drug, action taken with the study drug, outcome, and whether the event is classified as serious.

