7.2.5 Week 26 Visit (Visit 5, Day 182)

The following procedures will be performed at Week 26 (Day 182±3 days) of the study:

- AE review
- Concomitant medications review
- Plasma sample for measurement of SUVN-502, M1 of SUVN-502, donepezil and memantine levels
- Study drug compliance check and dispensation
- Blood and urine samples for clinical laboratory tests, including pregnancy test for women of childbearing potential
- Physical and neurological examinations
- Blood pressure measurement
- MMSE
- ADAS-Cog
- CDR-SB, ADCS-ADL, NPI and C-SDD
- C-SSRS (since last visit version)
- ECG 3 hours post-treatment

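### The TEAE rule has no end, so AEs that start in the placebo washout and follow-up are tabulated with on-drug AEs under the SUVN-502 dose

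*SAP*

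**What the plan says.** **Start of the window.** SAP 4.8.2 states "An AE will be considered a TEAE if it begins on or after the first study drug dosing", and adds events that worsen after at least one dose. Protocol 6.2.1.2 is equivalent: "A treatment-emergent AE (TEAE) will be defined as an AE that begins or that worsens in severity after at least one dose of study drug". Neither text gives a last day.

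**Collection.** Protocol 6.2.1.4 collects AEs "until 14 days after the last study treatment administration", and says that washout placebo counts as study treatment for this purpose.

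**Treatment after Week 26.** Protocol 5.1.1: "During the single-blind placebo washout period (Weeks 27 to 30), all subjects will receive placebo".

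**Display.** The AE summaries in SAP 4.8.2 are by treatment group, with no split by study period. They report subjects with an event and total events. The only period rule leaves pre-treatment events out of the summaries.

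**Grouping.** SAP 4.4 places safety subjects by the treatment they actually received. A subject who took more than one study drug goes to the highest dose group taken.

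**Exposure.** SAP 4.8.1: "Extent of exposure will be calculated for the Treatment Period (up to Week 26"). The same section also summarizes the duration of participation with follow-up included.

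**The concern.** Read literally, these rules place an AE that starts on washout placebo, or in the two weeks after it, in the 50 mg or 100 mg column. It sits beside events that started on active drug, and no table separates the two. The event window and the extent-of-exposure window also end on different days.

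Two things are at stake. First, background events that start off drug are added to all arms, which pulls relative comparisons of on-drug risk towards 1. Second, an excess that appears only after the drug is stopped would show in the TEAE tables as if it belonged to treatment with that dose. SAP 4.7.1.3 plans no formal safety tests and has AEs interpreted clinically, so these tables are the main comparative AE evidence on the two doses.

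**Working it through.** The plan states no number on this point, so there is no figure to reproduce. The window lengths follow from its schedule. The event rates and ratios below are assumptions, used only to show size.

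**Inputs from the documents**
- End of double-blind treatment: Day 182 (Protocol 7.2.5).
- End of washout and last scheduled visit: Day 210 (Protocol 7.2.6).
- AE collection: 14 further days (Protocol 6.2.1.4).
- Mean SUVN-502 half-life: 13.7 h at 50 mg and 12.5 h at 100 mg (Protocol 1.1.3). No half-life for M1 appears in the available text.

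**Window length for a completer**
- To Day 210: 210 − 182 = 28 days after double-blind treatment; 28/210 = 13.3%.
- To Day 224 (182 + 28 + 14): 42 days; 42/224 = 18.75%.
- Five half-lives of the parent drug: 5 × 13.7/24 = 2.9 days and 5 × 12.5/24 = 2.6 days. On the parent drug alone, most of the 28 to 42 days is off drug. M1 could lengthen the on-drug part.

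**Event counts.** Assume a constant background rate and a drug effect that acts only to Day 182. With true on-drug ratio R, the tabulated ratio is (182R + off-drug days) / (182 + off-drug days).

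| True R | Window to Day 210 | Window to Day 224 |
|---|---|---|
| 1.5 | (273 + 28)/210 = 1.43 | (273 + 42)/224 = 1.41 |
| 2.0 | (364 + 28)/210 = 1.87 | (364 + 42)/224 = 1.81 |
| 3.0 | (546 + 28)/210 = 2.73 | (546 + 42)/224 = 2.63 |

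**Early stoppers.** Assume 20% stop at Day 91 on average and have 14 days of collection afterwards. The off-drug share is (0.8 × 42 + 0.2 × 14)/(0.8 × 224 + 0.2 × 105) = 36.4/200.2 = 18.2%, and a ratio of 2.0 appears as 1.82. This is close to the completer figure.

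**Subjects with an event.** Incidence is 1 − exp(−hazard × time). Assume 5% placebo incidence by Day 182 and an on-drug hazard ratio of 2.

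| Window ends | Placebo | SUVN-502 | Risk ratio | Difference (points) |
|---|---|---|---|---|
| Day 182 | 5.00% | 9.75% | 1.95 | 4.75 |
| Day 210 | 5.75% | 10.46% | 1.82 | 4.71 |
| Day 224 | 6.12% | 10.81% | 1.77 | 4.69 |

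For placebo risks of 2% to 20% at the same hazard ratio, the risk ratio falls from 1.98–1.80 (Day 182) to 1.79–1.63 (Day 224). The risk difference keeps 95% to 99% of its size.

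**Excess only after stopping.** Assume no on-drug effect, a hazard ratio of 3 over the 42 days after the last active dose, and 5% placebo incidence by Day 182. Incidence to Day 224 is then 6.12% on placebo and 1 − 0.95^((182 + 3 × 42)/182) = 8.31% in the dose arm. The risk ratio is 1.36, against 1.00 for a window that ends at Day 182.

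**The case against.** A reader might infer that the open window dilutes any safety signal. The documents do not support that. The same rule applies to every arm, so extra background events lower ratios modestly and leave risk differences almost intact. The SAP plans numbers and percentages for AEs, not ratios. A withdrawal or delayed effect is added to the dose arm, not diluted.

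A reader might also infer that washout effects cannot be seen at all. That goes too far. SAP 4.8.2 lists AEs by treatment group with onset dates. Laboratory, blood pressure, ECG, examination and suicidality results are summarized by visit, and Week 30 is one of the scheduled visits. What is missing is a comparative AE table by period. Nor does the available text say what the washout is for, so the plan cannot be faulted for failing a stated aim.

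Three further points stand:
- The 19% is a ceiling. The last scheduled visit is Day 210, and no contact is planned in the 14 days after it, so 13% is the more realistic figure for completers.
- The exposure mismatch is partial, because SAP 4.8.1 also summarizes participation time that includes follow-up.
- The parent half-life alone cannot set the boundary. M1 binds the receptor more tightly than the parent (Ki 1.28 against 2.16 nM, Protocol 1.1.2.1). Its exposure also rises 1.6- to 2.5-fold from Day 1 to Day 14 (Protocol 1.1.3).

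Finally, an inclusive window is a defensible choice because it misses no delayed event. That argues for keeping the overall table. It does not argue against adding a split by period.

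**Conclusion.** The point holds in a limited form. Neither document ends the TEAE window, and no other section supplies an end. Followed as written, the plan tabulates off-drug events under the SUVN-502 dose: 13% of a completer's window to Week 30, and at most 19% with the 14-day tail.

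The distortion of on-drug comparisons is modest. An event-count ratio of 2.0 appears as 1.87 to 1.81, and risk differences barely move. Both results rest on an assumed constant background rate and a drug effect that stops with the last active dose. The less predictable consequence is misattribution: an effect that starts after stopping would look like an on-drug effect in the tables, and its size cannot be derived from the documents. This is a worthwhile, inexpensive clarification. It does not invalidate the planned safety analysis.

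**What to change.** In SAP 4.8.2, keep the overall TEAE table if wanted and add two displays:

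1. **Double-blind-period TEAEs:** onset or worsening from the first dose to the last double-blind dose plus a pre-specified lag. Justify the lag from the elimination of both SUVN-502 and M1. The M1 half-life has to be taken from the sponsor's phase 1 data, since the available text does not give it.
2. **Washout and follow-up AEs:** onset after that boundary.

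Show both by safety-population treatment group (actual treatment, as in SAP 4.4). State where an event that starts on drug and worsens after the boundary is counted, and whether study drug in the TEAE rule includes washout placebo.

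The cost is SAP wording and one extra set of AE tables from dates already collected. The lag involves judgement and must be fixed before unblinding.

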4.5.3 Concomitant Medications

Study medications will be coded using the World Health Organization (WHO) Drug dictionary version Sep2015 (WHODDE+HERBAL). Medications and all information collected will be reported as collected via the eCRF.

Prior medications are medications defined as those that stop before the first dose.

Concomitant medications (CMs) are medications taken during the study, including any medication that was ongoing at the time of first dose, medication taken on or after the first dose of study drug, or any medication started prior to the last treatment dose.

Partial date rules for flagging concomitant medications will follow the rules detailed in the AEs. In case of missing dates, a medication will be considered as concomitant.

A summary of CMs will be presented as frequencies and percentages for each treatment group and overall.

Prior and CMs will also be listed.

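### SAP 4.8.2 imputes partial adverse-event start dates without looking at the stop date, so an event known to have ended before the first dose can be counted as treatment-emergent

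*SAP*

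**What the plan says.** **Adverse events (SAP 4.8.2).** The definition turns on onset or worsening: "An AE will be considered a TEAE if it begins on or after the first study drug dosing", or worsens after at least one dose. A default follows for unclear timing: "In case of insufficient information to determine if the event occurred before, during or after study drug dosing, the AE will be considered treatment-emergent". The start-date rules then are:

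- Day missing, month and year equal to those of the first dose: "then day will be set to the same day as the start of study drug"; otherwise the first of the month.
- Month missing, year equal to that of the first dose: "then month will be set to the same month as the start of study drug"; otherwise January.
- Year missing: "If the year is missing, the event will be considered as treatment emergent and no imputation of the date will occur".

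Partial stop dates are imputed late: last day of the month, then December, and ongoing if the year is missing. Item 3 of the General Rules keeps pre-treatment events out of the summaries and puts them in a listing.

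**Medicines (SAP 4.5.3).** "Prior medications are medications defined as those that stop before the first dose". Concomitant medicines are those taken in the course of the study. The text says this includes three groups: medicines ongoing at first dose, medicines taken on or after first dose, "or any medication started prior to the last treatment dose". For incomplete dates, "Partial date rules for flagging concomitant medications will follow the rules detailed in the AEs", and a medicine with missing dates is treated as concomitant. Only concomitant medicines are summarised in a table; prior medicines are listed.

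**The concern.** Imputing an unclear onset towards treatment is ordinary and sensible when the timing is unknown. Here the rule also fires when the timing is known. If the stop date lies before the first dose, the event cannot have begun or worsened on study drug, yet the start-date rules can still place its onset on the first-dose day.

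The situation can arise. Adverse events are collected from consent (Protocol 6.2.1.4), and screening takes place 14 to 28 days before baseline (Protocol 7.2.1), so there is a pre-dose window in which events can start and resolve.

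At stake are the accuracy of the TEAE tables and of the onset and duration columns in the listings. To a lesser degree, so is whether the concomitant-medication table is limited to medicines in use during treatment.

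**Working it through.** The documents give no figure on this point, so the check is to apply the rules as written.

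**Step 1: adverse-event rules on invented records.** First dose 20 June 2016. Duration is taken as stop − start + 1. Where day and month are both missing, the month is imputed first and the day rule then applied; the SAP does not state the order.

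| Recorded start | Recorded stop | Start used | Classification | Duration (days) |
|---|---|---|---|---|
| 10 June 2016 | 14 June | 10 June | not TEAE (right) | 5 |
| May 2016, day missing | 30 May | 1 May | not TEAE (right) | 30 |
| June 2016, day missing | 14 June | 20 June | TEAE (wrong) | 14 − 20 + 1 = −5 |
| 2016, day and month missing | 30 May | 20 June | TEAE (wrong) | −21 + 1 = −20 |
| year missing | 14 June | none | TEAE (wrong) | none |

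Complete start dates, and partial dates in an earlier known month, are classified correctly. The error is confined to partial starts in the first-dose month or year and to missing start years.

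**Step 2: how often the rule fires, given a partial date.** Assume onsets are spread evenly over screening and first doses over the 366 days of 2016. With screening of S days, a first dose on day k of a month leaves S − k + 1 onset days in the previous month, for k = 1 to S. That is S(S + 1)/2 per month.

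- S = 14: 14 × 15/2 = 105 per month. Share in the first-dose month = 1 − (12 × 105)/(366 × 14) = 1 − 1,260/5,124 = 75%.
- S = 28: 28 × 29/2 = 406 per month. Share = 1 − (12 × 406)/(366 × 28) = 1 − 4,872/10,248 = 52.5%.
- Day and month both missing: only onsets in the previous calendar year escape, so the shares are 1 − 105/5,124 = 98% and 1 − 406/10,248 = 96%.

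Events that resolve before the first dose will tend to start earlier in screening, so these shares are probably somewhat high for them.

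**Step 3: illustrative count.** The documents give no rate of screening events or of partial dates. Suppose 10% of 537 subjects have an event that resolves before Day 1, and 10% of these events lack only the start day.

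- 537 × 0.10 × 0.10 = 5.37 events at risk.
- 5.37 × 0.525 = 2.8 and 5.37 × 0.754 = 4.0 wrongly flagged, or 0.9 to 1.3 per arm.
- The count is proportional to each assumed rate: halving one gives 1.4 to 2.0 events in total, and doubling one gives 5.6 to 8.1.

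**Step 4: medicines.** Take a medicine in use at screening and stopped a few days before first dose. It stopped before the first dose, so it is prior. It was taken during the study and started before the last dose, so it also meets the third concomitant group. A medicine with a missing start and a known pre-dose stop is prior by its stop date and concomitant by the missing-date default. Neither the third group nor that default refers to the stop date.

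**The case against.** On adverse events, the best reply is that the SAP already has the answer. The treatment-emergent default is limited to insufficient information, and General Rules item 3 keeps pre-treatment events out of the tables. The principle is indeed there, but the start-date rules do not defer to it, and a program that follows them literally will not apply it.

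Upstream controls also count. The protocol requires onset and resolution dates for every event (6.2.1.4) and provides queries and plausibility checks (9.2.1, 9.4), so partial dates should be few. That limits the size but does not correct the rule. It is also fair that the SAP does not say whether listings show imputed dates or use them for duration, so negative durations are possible rather than certain.

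On medicines, a reader might infer from the third group that every prior medicine is also concomitant, including those stopped in the 3 months before screening, so that the table would show everything recorded. The documents do not support this. The three groups illustrate an opening condition that the medicine was taken during the study, and on its natural reading that removes medicines stopped before screening. Prior medicines are also defined by stop date. What remains is the overlap in Step 4.

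**Conclusion.** The point holds for adverse events and, in a narrower form, for medicines. As written, the start-date rules can classify an event with a known pre-dose stop as treatment-emergent, against two other statements in the same section. The medication wording allows a prior/concomitant overlap for medicines stopped between screening and first dose, and for those with a missing start and a known pre-dose stop.

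The size is small. The count of roughly one event per arm rests entirely on assumed rates; the documents do not allow it to be derived. A reader might also infer that the comparison between arms is diluted or biased. That is not supported at this size: the rules apply identically in every arm, and safety is interpreted clinically without formal testing (SAP 4.7.1.3). The efficacy analyses are unaffected. This is a worthwhile tidy-up, not a threat to the trial's conclusions.

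**What to change.** In SAP 4.8.2, add after the start- and stop-date rules: *If the recorded stop date, or the stop date imputed to its latest possible value, is before the first dose, the event is not treatment-emergent, and an imputed start date may not fall after the stop date.* State that this also governs events with a missing start year.

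In SAP 4.5.3, add: *A medicine whose recorded or latest possible stop date is before the first dose is prior only; this overrides both the third group of the concomitant definition and the missing-date default.* Rewording the third group alone would leave the missing-date default in place.

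The cost is a sentence or two in each section and one condition in each derivation program. Because partial stop dates are already pushed to their latest possible value, nothing that could have overlapped with treatment is lost. If the text is left as it is, programmers must either follow it and accept these records, or depart from it and document the deviation in the study report, as SAP 4.2 requires.
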